Non-invasive imaging of neuroinflammation in living human subjects can be accomplished through the use of PET radioligands that target the TSPO. TSPO is a mitochondrial protein that is highly expressed in inflammatory cells including activated microglia in the brain. Previous PET studies from our laboratory using a TSPO radioligand, [¹¹C]PBR28, found significant correlations between brain uptake and clinical severity/progression of AD (Kreisl *et al*, 2016; Kreisl *et al*, 2013). Moreover, distribution of TSPO uptake in brain showed high correspondence with different clinical subtypes of AD that have distinct spatial patterns in their pathology (Kreisl *et al*, 2017). Small cross-sectional PET neuroinflammation imaging studies in FTD patients have been performed using 1st and 2nd generation TSPO radioligands (reviewed by Zhang, 2015). Overall, these studies saw increased TSPO radioligand uptake in FTD patients compared to control, with anatomical correlation between regional radioligand uptake and brain atrophy (Zhang, 2015).

We also performed a clinical [¹¹C]PBR28 PET study in patients with FTD. All patients met revised criteria for frontotemporal dementia (Neary *et al*, 1998). Five patients were included (age 53.4 ± 5.9 years). Four patients met clinical criteria for behavioral variant FTD, while one patient met criteria for progressive nonfluent aphasia. Thirteen older controls (age 64.0 ± 5.0 years) were included for comparison. Patients in general showed increased [¹¹C]PBR28 binding in frontal cortex, which in many cases was evident on visual inspection (Fig 1). Using a region-of-interest analysis and correcting for age, sex, education, and TSPO genotype, FTD patients had 42% greater [¹¹C]PBR28 binding (distribution volume corrected for free fraction of radioligand in plasma, V_T/f_P) than controls in prefrontal cortex ($p = 0.034$) and 45% greater binding in striatum ($p = 0.025$). These results suggest that FTD is associated with activation of microglia, similar to that seen in Alzheimer's disease (Kreisl *et al*, 2013); albeit with different regional distribution. Regions of increased [¹¹C]PBR28 binding in FTD patients correspond to those with expected neurodegeneration.

[figure not shown]

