9. OUTCOME MEASURES

a. Primary outcome measures

Difference of [¹¹C]ER176 brain uptake between healthy controls and neurodegeneration subjects.

b. Secondary outcome measures

- 1) Disease-specific patterns of [¹¹C]ER176 TSPO brain uptake across different neurodegenerative diseases.

The clinical phenotype of individuals with neurodegenerative diseases differs based on disease subtype, which in turn reflects differences in regional neurodegeneration across disease subtypes. For example, patients with AD usually exhibit prominent degeneration in the parietal cortex and hippocampus, individuals with FTD usually exhibit degeneration in the frontal and/or temporal lobes, and individuals with ALS exhibit motor cortex degeneration. Because previous studies with 1st and 2nd generation TSPO ligands have shown anatomical correlation between areas of cortical neurodegeneration and increased TSPO ligand uptake, we anticipate that our 3rd generation TSPO ligand will reveal anatomical differences in ligand uptake across different neurodegenerative diseases. We will quantify TSPO signals in pre-selected brain regions (for example, parietal cortex, temporal cortex, frontal cortex, motor cortex) in each individual, and compare regional TSPO uptake across different brain regions as a function of disease subtype. Voxel-based morphometry analysis of cortical neurodegeneration will be used to determine if TSPO uptake correlates anatomically with regional neurodegeneration.

- 2) Longitudinal imaging of individual patients shows a correlation between interval change of tracer uptake and disease progression.

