10. STATISTICAL ANALYSIS

a. Analysis of data/ study outcomes

PET and MRI scans will be coregistered for anatomic definition of regions of interest. SUV will be calculated in various brain regions. Parametric images will be created using PMOD software (PMOD Technologies Ltd., Zurich, Switzerland). Brain imaging data and/or blood data will be analyzed with compartmental modeling to achieve quantitation of each radioligand's target binding (e.g. V_T , V_T/f_P , SUV ratio) using PMOD software. Cross-sectional or longitudinal group comparison and correlation analysis with other clinical parameters will be conducted in each brain region using either regions-of-interest or voxel-based image analysis method. Statistical analyses will include ANCOVA for cross-sectional comparison among groups, and multilevel mixed model for longitudinal comparison among groups.

b. Power analysis

This study is exploratory and we do not know how much would [¹¹C]ER176 brain uptake be different between dementia patients and healthy subjects. Thus, a formal power calculation is impossible. We request accrual ceiling of 100 subjects with a diagnosis or with an increased risk of an age-related neurodegenerative diseases and 100 age and sex-matched healthy volunteers. Dropouts will not be replaced.

With regard to the interim analysis in cross-sectional part of this study, we plan to collect approximately 10-15 subjects in each of two groups: healthy controls and patients with neurodegenerative diseases. In our previous data from five FTD patients and control subjects scanned with [¹¹C]PBR28, which is an older generation TSPO radioligand, the estimated effect size was 0.50-0.65 in ANCOVA with TSPO genotype and demographic factors as covariates at a significance level of 0.05. If we assume [¹¹C]ER176 has the same effect size and variability with [¹¹C]PBR28, 10-15 subjects in two groups could achieve 79-93% power in the same statistical condition by G*Power program (v 3.0, University of Düsseldorf, Germany).

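### Regional uptake is compared, correlated with atrophy and followed over time in cortex expected to shrink, with no partial-volume analysis, so tissue loss can be mistaken for a TSPO effect

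*Combined protocol and SAP*

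**What the plan says.** Section 9.b (Secondary outcome measures) links each disease to a site of degeneration: parietal cortex and hippocampus in AD, frontal and/or temporal lobes in FTD, motor cortex in ALS. It expects TSPO uptake to follow the same anatomy. Its examples of regions for measurement are parietal, temporal, frontal and motor cortex, which are largely the cortices expected to shrink. It then states: "Voxel-based morphometry analysis of cortical neurodegeneration will be used to determine if TSPO uptake correlates anatomically with regional neurodegeneration". Morphometry is therefore a variable to be correlated with uptake, not a correction of it.

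Section 10.a (Analysis of data/study outcomes) says "PET and MRI scans will be coregistered for anatomic definition of regions of interest". It lists SUV, V_T, V_T/f_P and SUV ratio as possible measures, ANCOVA for group comparisons and a multilevel mixed model for longitudinal ones. Section 4.a adds atrophy pattern as an aid to differential diagnosis. Partial-volume correction, regional volume as a covariate, and a corrected-versus-uncorrected comparison appear nowhere.

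The planning figures come from an older tracer. In Section 1, "FTD patients had 42% greater" binding in prefrontal cortex than controls, and the excess in striatum was 45%. In Section 10.b "the estimated effect size was 0.50-0.65 in ANCOVA", and the longitudinal calculation assumes a rise of about 20% in 2.7 years. The documents do not say whether any of these figures was corrected for atrophy.

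**The concern.** A region's PET signal depends on tracer binding per unit of tissue and on how much tissue the region holds. When cortex thins, surrounding space is averaged in and the measured value drops even if binding per unit of tissue is unchanged. The protocol expects uptake to rise where tissue is being lost, so two opposing effects act on one number and the plan does not separate them.

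Four planned results are exposed: the patient-control difference, the disease-specific patterns, the uptake-atrophy correlation and the longitudinal change. The correlation is a particular problem because tissue loss enters both sides of it: it is the morphometry measure and it also lowers measured uptake.

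The other safeguards do not reach this. Recruiting "100 age and sex-matched healthy volunteers" balances age and sex, not disease-related atrophy. Kinetic modelling with a blood input accounts for tracer delivery, not for the fraction of a region that is tissue.

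**Working it through.** **The plan's own figure.** Section 10.b says "10-15 subjects in two groups could achieve 79-93% power in the same statistical condition", "with TSPO genotype and demographic factors as covariates at a significance level of 0.05". I read the effect size as Cohen's f (the metric is not stated) and used the noncentral F with df1 = 1, df2 = N - 2 - covariates, and noncentrality f² x N.

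| f | N = 20, 0 / 4 covariates | N = 30, 0 / 4 covariates |
|---|---|---|
| 0.65 | 78.5% / 77.1% | 93.0% / 92.7% |
| 0.50 | 56.2% / 54.8% | 75.3% / 74.8% |

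The stated 79-93% is reproduced at f = 0.65, the top of the quoted range. It does not arise at 0.50.

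**Illustration of the bias.** Let E be the true relative excess in patients and L the share of regional signal lost in patients relative to controls. Then measured excess = (1 + E)(1 - L) - 1. The documents give no value for L; 5-20% is an assumption.

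| L | True +42% reads as | True 0% reads as |
|---|---|---|
| 5% | 1.42 x 0.95 - 1 = +35% | -5% |
| 10% | 1.42 x 0.90 - 1 = +28% | -10% |
| 15% | 1.42 x 0.85 - 1 = +21% | -15% |
| 20% | 1.42 x 0.80 - 1 = +14% | -20% |

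The sign of a true +42% changes only if L exceeds 1 - 1/1.42 = 29.6%. For +45% the limit is 1 - 1/1.45 = 31.0%.

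L is signal loss, not volume loss. If 10% of tissue is lost but its space still carries half of the control signal, +42% reads as 1.278 + 0.5 x 0.10 - 1 = +33%.

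**Disease patterns.** Suppose two diseases both have a true +42% in a region, with L = 5% in one and 20% in the other. They read as +34.9% and +13.6%, an apparent gap of 21 points where none exists. Conversely, a true +42% with L = 20% reads as 1.42 x 0.80 - 1 = +13.6%, and a true +20% with L = 5% reads as 1.20 x 0.95 - 1 = +14.0%. A real difference disappears.

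**Uptake-atrophy correlation.** Measured uptake is true uptake x (1 - L), and the morphometry measure increases with L. If true uptake were unrelated to atrophy, measured uptake would still fall as atrophy rises. The correlation is pushed down, against the positive association the protocol expects. The documents do not allow the shift to be sized.

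**Longitudinal change.** If the true rise is 20%, an additional loss of 5% gives 1.20 x 0.95 - 1 = +14%, and 10% gives 1.20 x 0.90 - 1 = +8%. Full cancellation needs 1 - 1/1.20 = 16.7%. With 1-3% loss per year (assumption) over 2.7 years, 1.20 x 0.99^2.7 - 1 = +17% and 1.20 x 0.97^2.7 - 1 = +11%.

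**The reverse case.** If the pilot's +42% was itself uncorrected, the measured excess stays +42%. The true excess would then be 1.42/0.95 - 1 = +49% at L = 5%, 1.42/0.90 - 1 = +58% at 10%, and 1.42/0.80 - 1 = +77.5% at 20%.

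**The case against.** The strongest reply has four parts.

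- **The planning figures may already include the loss.** Section 1 reports +42% as a measured difference and mentions no correction. If it was uncorrected, the attenuation is already in the effect size used in Section 10.b and the stated power is unaffected by it. This stands. A reader might infer that interim power falls below 79-93%, but that requires the pilot excess to be free of atrophy bias, which the documents do not say.
- **The formula may not fit.** Regions are drawn on MRI and may shrink with the cortex, so a given volume loss need not produce an equal signal loss. This stands as a limit on size. It does not show that the effect is absent, which is why the figures are only illustrative.
- **Correction is noisy and depends on the method.** This is a good reason not to make corrected uptake the main measure. It is not a reason to leave the corrected result out.
- **The study is exploratory, the method list is open, and the analysis can be done later.** The scans would indeed still exist. But nothing commits the study to a correction, and choosing one after seeing results invites selection. Section 4.a also lets the interim comparison change later data collection, and Section 1 presents the work as a step toward a biomarker for treatment trials.

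**Conclusion.** The omission is real, and correcting it is a cheap improvement. Differential grey-matter loss lowers measured uptake, and the plan has no analysis that separates this from TSPO density. Under the assumed 5-20% relative signal loss, a true +42% reads as +35% to +14%, and zero true difference reads as -5% to -20%. The actual size cannot be obtained from the documents.

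Three stronger readings are not supported:

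- **That the bias always runs toward zero.** This holds where true uptake is raised or rising, as the background expects. The primary objective in Section 2.a asks only whether uptake differs. With no true increase, the bias creates a decrease.
- **That only patients are affected.** Controls are age-matched and may be rescanned for up to five years, so they may lose tissue too. At-risk subjects, who count toward the patient accrual, may have little atrophy. What matters is the difference in loss between those compared.
- **That tissue loss would reverse the planned longitudinal rise.** At 1-3% per year the rise shrinks to between +17% and +11%. Cancelling it takes 16.7% additional loss.

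**What to change.** Keep uncorrected uptake as the main measure. In Section 10.a:

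- Name one MRI-based partial-volume correction method before the interim data are examined, using the grey-matter segmentation that the morphometry already needs.
- Report corrected estimates with confidence intervals beside the uncorrected ones for the group comparison, the disease patterns, the uptake-atrophy correlation and the longitudinal change.
- State that where the two disagree in an atrophied region, the uncorrected difference, decrease or null is not attributed to TSPO density alone.
- Do not read two non-significant results as evidence of no difference. At 10-15 per group, agreement between two nulls shows little, and the confidence intervals should carry the interpretation.

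The cost is extra image-processing time and corrected values that are noisier than the uncorrected ones. Table 1 already schedules MRI at every evaluation, so no scan, visit or radiation exposure is added.

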10. STATISTICAL ANALYSIS

a. Analysis of data/ study outcomes

PET and MRI scans will be coregistered for anatomic definition of regions of interest. SUV will be calculated in various brain regions. Parametric images will be created using PMOD software (PMOD Technologies Ltd., Zurich, Switzerland). Brain imaging data and/or blood data will be analyzed with compartmental modeling to achieve quantitation of each radioligand's target binding (e.g. V_T , V_T/f_P , SUV ratio) using PMOD software. Cross-sectional or longitudinal group comparison and correlation analysis with other clinical parameters will be conducted in each brain region using either regions-of-interest or voxel-based image analysis method. Statistical analyses will include ANCOVA for cross-sectional comparison among groups, and multilevel mixed model for longitudinal comparison among groups.

b. Power analysis

This study is exploratory and we do not know how much would [¹¹C]ER176 brain uptake be different between dementia patients and healthy subjects. Thus, a formal power calculation is impossible. We request accrual ceiling of 100 subjects with a diagnosis or with an increased risk of an age-related neurodegenerative diseases and 100 age and sex-matched healthy volunteers. Dropouts will not be replaced.

With regard to the interim analysis in cross-sectional part of this study, we plan to collect approximately 10-15 subjects in each of two groups: healthy controls and patients with neurodegenerative diseases. In our previous data from five FTD patients and control subjects scanned with [¹¹C]PBR28, which is an older generation TSPO radioligand, the estimated effect size was 0.50-0.65 in ANCOVA with TSPO genotype and demographic factors as covariates at a significance level of 0.05. If we assume [¹¹C]ER176 has the same effect size and variability with [¹¹C]PBR28, 10-15 subjects in two groups could achieve 79-93% power in the same statistical condition by G*Power program (v 3.0, University of Düsseldorf, Germany).

Power calculation for the longitudinal study is rather limited because we don't have any longitudinal preliminary data in FTD patients. If we assume that longitudinal [¹¹C]ER176 uptake change in FTD is almost similar to [¹¹C]PBR28 uptake change in AD (approximately 20% increase within 2.7 years) (Kreisl *et al*, 2016), a sample size of 100 could achieve 72-99% power at a significance level of 0.05 in a multilevel mixed model with 4 repeated measures in 5 groups (3 subgroups of FTD, AD, and healthy control group) by GLIMMPSSE Software v 2.0.

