Participants will undergo a general and neurological exam, a standard battery of neuropsychological tests to measure cognitive function, blood tests for analysis of TSPO polymorphisms, MRI of the brain, and PET imaging with the [¹¹C]ER176 TSPO radioligand and [¹¹C]PIB amyloid radioligand. Participants will be invited to return for repeat evaluations approximately 1, 2, and 3-5 years after their initial evaluation.

Outcome measures

Brain PET and MRI scans will be co-registered for anatomic definition of regions of interest, and SUV will be calculated in various brain regions. [¹¹C]ER176 PET data will be analyzed with compartmental modeling. [¹¹C]PIB PET and MRI data will be adjunctly used for segregating the collected data by disease subtype. For the primary objective, we will compare TSPO radioligand uptake of healthy controls compared to subjects with neurodegenerative diseases. For secondary objectives, we will determine if neuroanatomical regions of tracer uptake differ across different neurodegenerative disease subtypes, and if interval change of tracer uptake correlates with disease progression in longitudinal imaging of individual subjects.

Table of Contents

PRÉCIS:	3
LIST OF ABBREVIATIONS	5
1. INTRODUCTION AND BACKGROUND.	5
2. STUDY OBJECTIVES	9
3. SUBJECTS	9
4. STUDY DESIGN AND METHODS	11
5. MANAGEMENT OF DATA AND SAMPLES	17
6. ADDITIONAL CONSIDERATIONS	19
7. RISKS AND DISCOMFORTS	19
8. SUBJECT SAFETY MONITORING	21
9. OUTCOME MEASURES	22
10. STATISTICAL ANALYSIS	22
11. HUMAN SUBJECTS PROTECTION	23
12. BENEFIT	24
13. CONSENT DOCUMENTS AND PROCESS	24
14. DATA AND SAFETY MONITORING	25
15. QUALITY ASSURANCE (QA)	26
16. REPORTING OF UNANTICIPATED PROBLEMS, ADVERSE EVENTS AND PROTOCOL DEVIATIONS	26
17. ALTERNATIVES TO PARTICIPATION	27
18. PRIVACY	27
19. CONFIDENTIALITY	27
20. CONFLICT OF INTEREST	27
21. RESEARCH AND TRAVEL COMPENSATION	28
22. REFERENCES	29

LIST OF ABBREVIATIONS

AD	Alzheimer's disease
ALS	amyotrophic lateral sclerosis
C9ORF72	chromosome 9 open reading frame 72
DLB	dementia with Lewy bodies
FTD	frontotemporal dementia
GRN	progranulin gene
HAB	high-affinity binder
IL	interleukin
LAB	low-affinity binder
MAB	mixed-affinity binder
MND	motor neuron disease
MRI	magnetic resonance imaging
PBR	peripheral benzodiazepine receptor
PD	Parkinson's disease
PGRN	progranulin protein
PET	positron emission tomography
PIB	Pittsburgh compound B
SUV	standardized uptake value
TBK1	TANK-binding kinase 1
TNF	tumor necrosis factor

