Fig 1. Representative [¹¹C]PBR28 parametric images (V_T/f_P) for a patient with behavioral variant FTD and a healthy control. Both subjects are high affinity binders (non-carriers of the rs6791 TSPO polymorphism). Arrows show increased binding in frontal and temporal cortices.

However, 1st and 2nd generation suffer from reduced uptake in a significant fraction of the human population that carry a single nucleotide polymorphism (rs6791) in the *TSPO* gene, making it difficult if not impossible to analyze scans obtained from such patients. Second, the sensitivity and specificity of 1st and 2nd TSPO radioligands is relatively poor compared to third generation radioligands. Finally, few longitudinal studies of TSPO PET imaging in patients with neurodegeneration have been performed, especially rare forms of neurodegeneration such as

FTD. Such studies are needed to determine if PET imaging of neuroinflammation may be a suitable biomarker for future treatment trials.

We recently developed a new 3rd-generation radioligand binding for TSPO, [¹¹C]ER176, which showed excellent brain uptake in eight healthy subjects as shown in Fig 2 (Ikawa *et al*, 2017). An apparently unique advantage of [¹¹C]ER176 compared to conventional TSPO radioligands is that it provides quantifiable distribution volume (V_T) regardless of single nucleotide polymorphism rs6971 in the *TSPO* gene. Specifically, with other TSPO radioligands, all subjects must be pre-screened by genetic tests, and low-affinity binders (LABs) must be excluded from PET scans because the brain has too little uptake to quantify. In contrast, a similar pre-screening and exclusion process is unnecessary for [¹¹C]ER176 because even LABs have substantial V_T values in their brain (Fig 3). It should be noted that although subjects need not be excluded a priori, the results must be corrected for genotype *a posteriori*. This provides particularly significant advantage in the present study, since our potential participants are those having rare disorders with severe disability, additional screening for exclusion of TSPO LABs may result in too limited number of subjects for meaningful interpretation, especially in rare disease subtypes such as FTD or in genetically-defined familial cases.

[figure not shown]

Fig 2.

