2. STUDY OBJECTIVES

a. Primary objectives

We will explore if human subjects with neurodegenerative diseases exhibit different brain uptake levels of the [^{11}C]ER176 TSPO ligand compared to control subjects.

b. Secondary objectives

We will explore if,

- 1) [^{11}C]ER176 TSPO brain uptake shows disease-specific patterns across different neurodegenerative diseases
- 2) Longitudinal imaging of individual patients shows that interval changes in tracer uptake correlate with disease progression.

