3. SUBJECTS

a. Description of study populations

- Adults with a diagnosis or with an increased risk of FTD, ALS, AD, or a related adult-onset neurodegenerative disease
- Accrual ceiling of 100 patients with age-related neurodegenerative diseases or subjects with genetically increased risk of such diseases, and 100 healthy volunteers who are matched for age (± 5 years) and sex
- Dropouts will not be replaced
- NIH employees may participate if they meet the eligibility criteria, but NIMH employees/staffs or NIH employees who are subordinates/relatives/co-workers of investigators may not participate.

b. Inclusion criteria

- 1) Patients will be included if they
 - Are age 18 or older

- Have the ability to understand and sign an informed consent, or have a DPA or a court-appointed guardian (or be able to understand the DPA process to appoint a DPA) to provide consent for adults without consent capacity
- Have been given a diagnosis by a neurologist of frontotemporal dementia, frontotemporal lobar degeneration, primary progressive aphasia, semantic dementia, motor neuron disorder, amyotrophic lateral sclerosis, primary lateral sclerosis, progressive bulbar palsy, corticobasal syndrome, Huntington disease, Alzheimer's disease, or other related adult-onset neurodegenerative disease

- 2) Subjects with an increased risk of neurodegenerative diseases will be included if they
 - Are age 18 or older
 - Are able to give written informed consent
 - Have known family history or other risk of an adult-onset genetic neurodegenerative disease, and/or mutation in a gene known to cause an adult-onset neurodegenerative disease
- 3) Healthy subjects will be included if they
 - Are age 18 or older
 - Are willing and able to complete all study procedures
 - Are able to give written informed consent
 - Are medically healthy
 - Are enrolled in 01-M-0254 "The Evaluation of Participants with Mood and Anxiety Disorders and Healthy Volunteers" (PI: [name]) or 17-M-0181, "Recruitment and Characterization of Healthy Research Volunteers for NIMH Intramural Studies" (PI: [name])

c. Exclusion criteria

- 1) Patients or subjects with an increased risk of neurodegenerative diseases will be excluded if they

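### Secondary objective 1 asks whether the regional pattern of uptake differs by disease, but Section 10.a names no group-by-region test

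*Combined protocol and SAP*

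**What the plan says.** The question is put three times. Section 2.b asks whether "TSPO brain uptake shows disease-specific patterns across different neurodegenerative diseases". The Précis (Outcome measures) says "we will determine if neuroanatomical regions of tracer uptake differ across different neurodegenerative disease subtypes". Section 9.b is the most specific: it will quantify signal in pre-selected regions, offering parietal, temporal, frontal and motor cortex as examples, and "compare regional TSPO uptake across different brain regions as a function of disease subtype". In statistical terms that is a disease-by-region comparison.

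Section 10.a is the analysis text. Group comparison and correlation analysis "will be conducted in each brain region using either regions-of-interest or voxel-based image analysis method". It then states: "Statistical analyses will include ANCOVA for cross-sectional comparison among groups, and multilevel mixed model for longitudinal comparison among groups".

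Section 9.b adds one further regional analysis: "Voxel-based morphometry analysis of cortical neurodegeneration will be used to determine if TSPO uptake correlates anatomically with regional neurodegeneration".

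**The concern.** Section 9.b states a comparison between regions as a function of disease. Section 10.a plans comparisons within each region. The two answer different questions: a significant difference in frontal cortex and a non-significant one in parietal cortex do not show that the two regions differ from each other. If two diseases differ by the same amount everywhere, sampling error alone will often leave some regions below 0.05 and others above it, and the resulting map can look disease-specific.

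At stake is the reading of objective 1. Section 10.a names no test that would tell a uniform difference from a regional one, and no rule for combining regional results into a pattern.

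**Working it through.** **1. Does any named analysis fill the gap?** The document gives no figure for the pattern comparison, so there is nothing to reproduce and the check starts with the text.
- ANCOVA is named for cross-sectional comparison among groups, with the region as the unit of analysis.
- The multilevel mixed model is tied to longitudinal comparison. The four repeated measures in Section 10.b match the four evaluations in Table 1, so they are time points, not regions.
- Voxel-based analysis is offered as another way of making the same per-region comparison.
- Voxel-based morphometry asks whether uptake follows atrophy, not whether diseases differ in pattern.
- The power text covers the two-group interim comparison and the longitudinal model only.

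**2. How often is significance mixed when there is no pattern?** Inputs: four regions (the examples in Section 9.b); level 0.05 (Section 10.b), taken as two-sided. Assumed: the same true effect in every region, 50% or 80% power per region, and equal inter-region correlation ρ of 0.5 to 0.9.

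Model: z_j = μ + √ρ·u + √(1−ρ)·e_j, with u and e_j standard normal and μ set to give the stated power. The quantity is P(some but not all |z_j| > 1.96), from 500,000 draws.

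| Regions | Power per region | ρ = 0.5 | 0.7 | 0.8 | 0.9 |
|---|---|---|---|---|---|
| 2 | 50% | 33% | 25% | 20% | 14% |
| 2 | 80% | 22% | 17% | 14% | 10% |
| 4 | 50% | 60% | 46% | 37% | 26% |
| 4 | 80% | 41% | 32% | 26% | 18% |

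Hand check for two regions at 50% power: P(both) = 1/4 + arcsin(ρ)/(2π). At ρ = 0.5 this is 0.333, so mixed = 2 × (0.5 − 0.333) = 0.333, as in the table.

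**3. Does an interaction test behave as needed?** Simulated log uptake, two groups of 10 to 20, four regions, a uniform shift on the log scale, and genotype, age and sex entered with by-region terms (3,000 runs per setting). The multivariate profile test rejects in 4.5% to 5.4%. Mixed regional significance together with a significant interaction occurs in 1.6% to 4.3%. A mixed model with only a subject random effect rejects in 7% to 8% when inter-region correlations are unequal, hence the unstructured covariance in the fix.

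**4. What does the test cost in power?** One of k regions differs by d (in SD), with n per group and six design columns (intercept, group, two genotype indicators, age, sex). The affected region's own ANCOVA has noncentrality λ = n·d²/2. The interaction has λ·(1 − 1/k)/(1 − ρ), on k − 1 and (2n − 6) − (k − 1) + 1 degrees of freedom.
- n = 20, k = 4: own-ANCOVA power of 80% needs λ = 8.32, so d = √(2 × 8.32/20) = 0.91. At ρ = 0.2 the interaction has 8.32 × 0.75/0.8 = 7.80 on 3 and 32 df, which gives 58%. At ρ = 0.3, 0.4, 0.5 and 0.7 it gives 65%, 72%, 81% and 96%.
- n = 5, k = 4: only 4 error df remain. Power is 24% to 48% (ρ = 0.2 to 0.7), and only for d of about 2.4. At d = 0.91 it is about 8% to 13%.
- Three groups of 5, Pillai test, one group differing by 2.0 SD in one region (simulated): about 17% to 32% over the same range of ρ.
- k = 8, ρ = 0.5, own-ANCOVA power 80%: 69% at 20 per group and 48% at 10. At 5 per group it cannot be computed (7 contrasts, 4 error df).

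**The case against.** The strongest reply is that this is an exploratory study, objective 1 is secondary, and Section 9.b already states the right comparison in words. The methods list in Section 10.a is inclusive, and an ANCOVA with region as a within-subject factor would fit it. Section 10.a also lists SUV ratio among its measures. On the log scale a target-to-reference ratio is itself a between-region difference, although no reference region is named and the ratio may be meant for [¹¹C]PIB. All of this stands as a limit on weight: the model is unspecified, not excluded, and the question has not been overlooked. It does not supply a test.

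The harm is also conditional. No section says that objective 1 will be judged by counting significant regions, and the correlations and powers used above are assumptions. A reader might take 26% to 60% as the chance of a false finding of disease specificity; the document does not support that.

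A reader might also infer that age differences between disease groups will distort the pattern. The one age gap on record is in the Section 1 pilot: FTD patients at 53.4 years against controls at 64.0, or 10.6 years. That compares patients with controls under another radioligand. No age gap between diseases and no region-specific age slope is given, so no size can be put on this.

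Finally, the interaction has weaknesses of its own. It depends on scale. V_T includes nondisplaceable uptake, and a uniform absolute rise is not uniform in logs: with assumed baselines of 1.0 and 1.3, adding 0.2 to both is a 20% rise in one region and 15% in the other (0.2/1.3). Disease-specific atrophy that lowers apparent signal in one region can also produce an interaction. Both points stand and belong in the plan.

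**Conclusion.** The point holds as a cheap improvement to consider. Objective 1 and Section 9.b call for a between-region comparison by disease; Section 10.a names only within-region comparisons for cross-sectional data, and no group-by-region test appears anywhere. Confidence in that textual gap is high.

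The size is illustrative. The mixed-significance rates in step 2 depend on the assumed uniform effect, correlation and power. A positive interaction would show that the groups differ in profile on the chosen scale. It would not by itself show that inflammation, rather than scale or tissue loss, is the cause.

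**What to change.** In Section 10.a:
1. Close a short list of pre-selected regions, in place of the examples in Section 9.b.
2. Make the disease-group-by-region interaction on log uptake the test for objective 1, by a multivariate profile test on between-region differences or a mixed model with unstructured within-subject covariance.
3. Enter TSPO genotype, age and sex with their by-region terms. Subject-level main effects cancel out of within-subject contrasts, so alone they would leave the interaction unadjusted. Section 1 says "the results must be corrected for genotype", and Section 3.a provides for "100 healthy volunteers who are matched for age" and sex but states no matching between disease groups.
4. Report regional ANCOVAs and voxel maps as follow-up, and describe subtypes too small for the test without testing them.
5. State that the log scale tests for a uniform percentage difference, and read a positive result alongside the planned morphometry.

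The cost is wording and one added model on data already planned. The by-region covariate terms lose about 2 to 4 points of power at 10 per group, depending on how the effect is calibrated, and at most about 1 point at 15 to 20. The downsides to state are those in step 4: below a correlation of about 0.5 the test is less sensitive than the affected region's own ANCOVA, power is low in small subtypes, and each added region costs power.
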